***Statistical Analysis Plan***

**7**

**MEASUREMENTS OF TREATMENT COMPLIANCE**

Adherence to treatment comprises a secondary objective of the study and the relevant analysis is described in the Section 8.2

***Statistical Analysis Plan***

***Statistical Analysis Plan***

## **Statistical Analysis Plan**

## **9 SAFETY ANALYSES**

The analysis set that will be used for the safety analyses is described in Section 3.5.

### **9.1 Extent of exposure**

All afatinib treatment characteristics, including the age at afatinib treatment onset, the time elapsed from afatinib treatment onset to enrolment, the time elapsed from the diagnosis of locally advanced/metastatic NSCLC to afatinib initiation will be presented by the use of summary statistics.

Moreover, the duration on afatinib treatment (*as defined in Section 3.7*) as well as the length of exposure in afatinib during the observation period will be presented by descriptive statistics. The length of exposure in afatinib will be calculated by subtracting the intervals of temporary interruptions from the duration of afatinib treatment.

### **9.2 Adverse events**

The following adverse events are collected from the time the patient has signed the informed consent until the completion of his/her participation in the study: all serious and non-serious adverse drug reactions (ADRs) related to GIOTRIF; all AEs with fatal outcome (regardless of causal relationship with GIOTRIF); and all AEs (serious and non-serious) which are relevant to a serious ADR or to an AE with fatal outcome. An ADR is defined as a response to a medicinal product which is noxious and unintended. Response in this context means that a causal relationship between a medicinal product and an adverse event is at least a reasonable possibility.

All recorded adverse events will be mapped by LLT, PT and SOC according to MedDRA (the most updated version available at the time of coding onset). If two or more AEs (PTs) are reported as a unit, the individual terms will be reported as separate events.

A descriptive summary table will be created with the number and proportion of patients experiencing at least one adverse drug reaction regardless of seriousness (N)SADR, serious adverse drug reaction (SADR), non-serious adverse drug reaction (NSADR) and SAE. The percentage of patients who discontinued their treatment with afatinib due to AEs will also be tabulated.

Additionally, the following data will be provided in frequency tables:

## Statistical Analysis Plan

- ✓ Number and percentage of patients experiencing at least one (N)SADR by SOC and PT.
- ✓ Number and percentage of patients experiencing at least one SADR by SOC and PT.
- ✓ Number and percentage of patients experiencing at least one NSADR by SOC and PT.
- ✓ Number and percentage of patients experiencing at least one SAE by SOC and PT.

*The aforementioned analysis will also be performed by outcome and action taken with afatinib.*

- ✓ Number and percentage of patients experiencing at least one (N)SADR by SOC, PT and NCI CTCAE grade.
- ✓ Number and percentage of patients experiencing at least one SADR by SOC, PT and NCI CTCAE grade .
- ✓ Number and percentage of patients experiencing at least one NSADR by SOC, PT and NCI CTCAE grade .
- ✓ Number and percentage of patients experiencing at least one SAE by SOC, PT and NCI CTCAE grade .

A patient data listing of all reported AEs will also be created and presented. The listing will include information related to the reported events [i.e. patient ID, center ID, verbatim term of AE, MedDRA terms (LLT, PT, SOC), onset date of AE, end date, outcome, causal relationship with afatinib, NCI CTCAE grade, seriousness, action(s) taken].

Additionally, the exposure-adjusted incidence rates (EAIRs) along with the respective 95% CI will be calculated for those experiencing at least one (N)SADR, at least one SADR, at least one NSADR.

Specifically, the EAIR is defined as the number of patients with a specific event divided by the total exposure-time in subject-year:

$$EAIR = \frac{n}{\sum t_i} \times 100$$

where n is the number of patients with at least one event and  $t_i$  is a patient's follow-up in subject-years.

If a patient has multiple events, then  $t_i$  is defined as the time from treatment onset to the occurrence of the first event. For a patient without any event, the  $t_i$  will be censored at the last follow-up time for that patient. The respective 95% CIs will also be calculated as follows:

$$\text{Lower confidence limit: } LCL = \frac{0.5c_{\alpha/2,2D}}{T} \text{ for } D > 0, 0 \text{ otherwise}$$

$$\text{Upper confidence limit: } UCL = \frac{0.5c_{1-\alpha/2,2D+2}}{T},$$

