## ***Statistical Analysis Plan***

where  $\alpha=0.05$ , D is the number of subjects with at least one event and  $c_{\alpha,k}$  is the  $\alpha^{\text{th}}$  quantile of the  $\chi^2$  distribution with k degrees of freedom.

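### SAP 9.2 multiplies the exposure-adjusted incidence rate by 100 but not its 95% limits, and the limits divide by an undefined T

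*SAP*

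**What the plan says.** SAP 9.2 (Adverse events) plans EAIRs with 95% confidence intervals for patients with at least one (N)SADR, at least one SADR and at least one NSADR.

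- **Verbal definition.** The count of affected patients is "divided by the total exposure-time in subject-year". This has no factor of 100.
- **Displayed formula.** n over the sum of the t_i, times 100, "where n is the number of patients with at least one event and $t_i$ is a patient's follow-up in subject-years".
- **Limits.** The lower limit is "LCL = \frac{0.5c_{\alpha/2,2D}}{T} \text{ for } D > 0, 0 \text{ otherwise}" and the upper is "UCL = \frac{0.5c_{1-\alpha/2,2D+2}}{T}". Neither has a factor of 100.
- **Symbols.** The note below the limits sets alpha at 0.05, states that "D is the number of subjects with at least one event and" explains c as a chi-square quantile. T is not explained there or anywhere else in the SAP text available.
- **Time at risk.** "If a patient has multiple events, then" t_i runs from treatment onset to the first of them. A patient with no event is censored at last follow-up. A patient with exactly one event is not mentioned.

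Protocol 11.8.4 asks for EAIRs with 95% confidence intervals but gives no formula, so it does not settle the scale.

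**The concern.** A rate and its confidence limits must be in the same unit. With t_i in subject-years, the displayed EAIR is a rate per 100 subject-years. The limits are a chi-square quantile, halved, over T. If T is the sum of the t_i, they are per subject-year and so 100 times too small for the estimate beside them.

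The SAP does not show which side should change. The verbal definition matches the limits in scale; the displayed formula does not. A programmer could reasonably multiply the limits by 100 or drop the 100 from the estimate. If the formulas were coded literally, all three planned EAIRs would be printed with limits on another scale.

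The wording on time at risk raises a smaller question. Read literally, a patient with exactly one event keeps the general definition of t_i as follow-up time and so contributes time after the event, while a patient with two events does not.

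**Working it through.** The documents give formulas but no numerical EAIR or limit, so there is no planned figure to reproduce.

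**Inputs**
- EAIR = 100 × n / Σt_i, with t_i in subject-years (SAP 9.2).
- LCL = 0.5 × χ²(0.025; 2D) / T for D > 0, otherwise 0; UCL = 0.5 × χ²(0.975; 2D + 2) / T (SAP 9.2).
- D and n are the same count: patients with at least one event.
- D can be at most 128, the planned enrolment (SAP 2.3).
- Assumption: T = Σt_i in subject-years, the only exposure total the section contains.

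**Step 1: is the interval method sound?** Yes. At the values of D tried from 1 to 128, each exact Poisson tail at these limits equals 0.025. They are therefore the exact 95% limits for the unscaled rate D/T. For D = 10 they are 4.7954/T and 18.3904/T, which contain 10/T. The fault is one of scale only.

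**Step 2: compare the upper limit with the displayed EAIR.** T cancels:

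UCL / EAIR = 0.5 × χ²(0.975; 2D + 2) / (100 × D)

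| D | UCL as a percentage of the displayed EAIR |
|---|---|
| 1 | 5.5716 / 100 = 5.57% |
| 20 | 1.54% |
| 100 | 1.22% |
| 128 | 152.1924 / 12,800 = 1.19% |

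The ratio is largest at D = 1 and below 1 for every D from 1 to 128 (and on to 100,000), so the displayed EAIR always lies above its upper limit. At D = 0 the EAIR is 0 and the interval runs from 0 to 3.689/T, which does contain it.

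**Step 3: examples.** D and T here are assumed; the documents give neither.

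| D | T (subject-years) | Displayed EAIR | Limits as written | Limits × 100 |
|---|---|---|---|---|
| 5 | 150 | 3.3 | 0.011 to 0.078 | 1.1 to 7.8 |
| 20 | 150 | 13.3 | 0.08 to 0.21 | 8.1 to 20.6 |
| 60 | 80 | 75.0 | 0.57 to 0.97 | 57.2 to 96.5 |

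**Step 4: the other reading of T.** If T is in hundreds of subject-years, D = 20 and 150 subject-years give T = 1.5 and limits of 8.14 to 20.59, which agree with 13.33.

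**Step 5: the single-event wording.** Take D = 20 and T = 150, giving 13.3 when time stops at the first event. The further follow-up is assumed.
- 5 single-event patients with 0.25 further years each: 100 × 20 / (150 + 1.25) = 13.2.
- All 20 event patients with one event and 1.0 further year each: 100 × 20 / (150 + 20) = 11.8.

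**The case against.** The strongest reply is that this is a notation slip. The limits are plainly meant to belong to the displayed EAIR, and they do if T is in hundreds of subject-years. The exclusion therefore depends on how an undefined symbol is read. The study is descriptive, no decision rests on these rates, and an upper limit at 1% to 6% of its estimate would be noticed when the tables are checked.

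Most of this stands as a limit on importance. It does not remove the defect. The only unit the section states is the subject-year, so reading T in hundreds requires an unstated unit. A reader who notices the mismatch must still choose which side to correct, and the SAP supports either choice. Nor is the mismatch always obvious: limits of 0.57 to 0.97, as in the third example, could pass for proportions.

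On the single-event wording the reply is stronger. Censoring at last follow-up is given only for patients with no event, and a sole event is also a first event, so the usual time-to-first-event rule is very probably intended. The 11.8 figure rests on an extreme assumption. It remains true that the text does not state the rule for these patients, so this is a wording gap of minor weight.

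**Conclusion.** The concern holds. The factor of 100 is in the EAIR and absent from its limits, and T is undefined. Taking T as the sum of the t_i in subject-years, the limits are too small by a factor of 100 and exclude the displayed EAIR for every D from 1 to 128. This does not depend on total follow-up. D = 0 is the only exception.

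The effect is confined to three descriptive safety rates. The chi-square form is correct, and the primary endpoint, sample size and interim analysis are untouched. It should be fixed before the safety tables are programmed.

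**What to change.** In SAP 9.2:

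1. Define T as the sum of the t_i in subject-years.
2. Put estimate and limits on one scale: either multiply both limits by 100, or remove the factor of 100 from the EAIR. Align the verbal definition with that choice.
3. State the unit in the text and in the table header.
4. State that t_i ends at the first event for any patient with one or more events.

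The cost is one scaling constant, one symbol definition and a few words of clarification. No new data are needed, and treatment onset stays as the time origin.

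As a check on the scaled version, D = 10 with an assumed 100 subject-years should give an EAIR of 10.0 with limits 4.80 to 18.39 per 100 subject-years.

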## ***Statistical Analysis Plan***

where  $\alpha=0.05$ , D is the number of subjects with at least one event and  $c_{\alpha,k}$  is the  $\alpha^{\text{th}}$  quantile of the  $\chi^2$  distribution with k degrees of freedom.

### **9.3 Vital signs**

Summary statistics for heart rate (beats/minute), respiratory rate (breath/minute), systolic and diastolic blood pressure (mmHg) at enrolment as well as at post-baseline predefined time points will be calculated and presented along with the relevant changes from enrolment.

***Statistical Analysis Plan***

**11 APPENDICES**

N/A
